7.5. Respondent Monitoring

Monitoring of anthropometry and blood pressure

The subjects of the research will undergo physical monitoring, including weight, height, BMI, waist circumference and blood pressure, by research team on days 0 and 15 (one day before and one day after the last day of the white tea intervention).

Laboratory monitoring

Laboratory monitoring was conducted on days 0 and 15 (one day before and one day after the last day of the white tea intervention) on blood samples from subjects in order to determine the effects of drinking tea for a period of 14 days. Should the preliminary investigative results pertaining to haematological parameters (RBC, HB, HCT, MCV and MCH), ALT, AST, serum creatinine levels, eLFG and urea nitrogen levels demonstrate abnormality, the subject will be withdrawn from the study for reasons of safety. Haematological tests are performed to ensure that the subject is not anaemic. ALT and AST tests are performed to ensure that there is no liver dysfunction, while serum creatinine, eGFR, and urea nitrogen tests are performed to ensure that the subjects do not have kidney dysfunction. In summary, the parameters employed in this study to observe the effects of white tea consumption are outlined as follows:

- a. Hematology profile
- b. Lipid profil
- c. Fasting blood glucose
- d. ALT dan AST
- e. Serum creatinine level, urea nitrogen level and eGFR
- f. First line antioxidant enzymes (SOD, CAT dan GPx).

Monitoring consumption and daily activities

In order to ensure that respondents adhere to the prescribed dietary regime, researchers will ensure that subjects abstain from the consumption of particular products that must be avoided during the course of the research process. Researchers will record all food and beverages consumed, the subjects' daily activities, and any complaints that may be experienced by the subjects, whether related or unrelated to the administration of white tea products.

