7.7. Anthropometric Measurement

Measurements of body weight, height, and waist circumference for the study will be taken on day 0 (one day before the intervention) and day 15 (one day after the last day of the white tea intervention). Participants are advised to wear light clothing and remove their shoes before weight and height measurements. BMI values will be calculated using an online BMI calculator based on weight (kg) and height (cm) (nhlbi.nih.gov/health/education/lose_wt/BMI/bmi-m.htm).

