7.8. Blood Pressure Measurement

Concurrently, blood pressure assessments will be conducted on the day of blood sampling. The protocol for conducting blood pressure tests is outlined as follows:

- a. Participants are asked to rest for 5 minutes before blood pressure measurement without talking during the rest period.
- b. Participants are asked to sit upright with their back against the chair, ensuring that both feet are flat on the floor.
- c. Blood pressure measurement will be taken in a sitting position with the sleeve of the shirt open.
- d. The sphygmomanometer is placed on the right or left arm approximately 3 cm above the elbow crease. The arm cuff should not be too tight or too loose.
- e. The start button on the sphygmomanometer monitor is pressed. Blood pressure measurements will be taken three times, with a 1-minute interval between each measurement.
- f. The systolic and diastolic pressure results are recorded.

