APPENDIX 1. SCREENING FORM FOR SUBJECTS

SAMPLE

Research Number:	Respondent's initials: [] [] []
------------------	------------------------------------

SCREENING 1 – PERSONAL DATA

PERSONAL DATA		Officer ()
Date of data collection	: [] / [] / [] (DD/MM/YY)	
Name / initial	: [] [] []	
Place and Date of Birth		
Age	: Tahun	
Gender	: Pria / Wanita *	
Job	:	
Address	:	
Contact	:	

Note: The first two boxes in the initials are filled in with the first two letters of the two words of the name, and the third box is filled in with the date of birth. If the date of birth contains two numbers, use only one of them.

Example: Name: [name], Date of Birth: Januari 8th → [L|C|8].

MEDICAL HISTORY

History	Yes	No	Unknown
Have you ever had anaemia within the last 5 years?			
Do you have a history of kidney disorder?			
Do you have a history of stomach ulcers or GERD?			
Do you have a history of liver disorder?			
Are you an active smoker < 5 years?			
Are there any family members who smoke?			
Are you undergoing any medical treatment? Please specify!			

Signature of officer after filling out form:

Initials:

Date:

SAMPEL

Research Number:	Respondent's initials: []
------------------	---

SCREENING 2 – ANTHROPOMETRY AND BLOOD PRESSURE

ANTHROPOMETRIC EXAMINATION (PRE)	
Body weight : kg	Body height : cm
BMI : kg/m ²	
Waist Circumference: cm	
BLOOD PRESSURE MEASUREMENT (PRE)	
Blood pressure:	

ANTHROPOMETRIC EXAMINATION (POST)	
Body weight : kg	Body height : cm
BMI : kg/m ²	
Waist Circumference: cm	
BLOOD PRESSURE MEASUREMENT (POST)	
Blood pressure:	

Signature of officer after filling out form: Initials: Date:

SAMPEL

Research Number:	Respondent's initials: []
------------------	----------------------------

SCREENING 3 – BLOOD AND BIOCHEMICAL TESTS

a. Initial Screening

Parameters	Test Date/Time	Result	Status
Hematology Profile	[] / [] / [] (DD/MM/YY) [] . [] WIB	RBC : $10^6/\mu\text{L}$ HB : g/dL HCT : % MCV : fL MCH : pg	 Eligible  Not Eligible
Lipid Profile	[] / [] / [] (DD/MM/YY) [] . [] WIB	TC : mmol/L HDL : mmol/L LDL : mmol/L Tg : mmol/L	 Eligible  Not Eligible
Fasting Blood Glucose	[] / [] / [] (DD/MM/YY) [] . [] WIB	mmol/L	 Eligible  Not Eligible
ALT	[] / [] / [] (DD/MM/YY) [] . [] WIB	$\mu\text{kat/L}$	 Eligible  Not Eligible

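### Screening 2 records day-0 and day-15 waist and blood pressure on one form with one signature and date, so the baseline can be seen at day 15 and nothing in the protocol prevents it (minor)

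*Combined protocol and SAP*

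**What the plan says.** Section 7.5 has subjects physically monitored, "including weight, height, BMI, waist circumference and blood pressure, by research team on days 0 and 15". No independent or masked assessor is described there or elsewhere. Section 7.7 sets the timing: "Measurements of body weight, height, and waist circumference for the study will be taken on day 0 (one day before the intervention) and day 15". It covers light clothing, removal of shoes and the BMI calculator, but gives no landmark, tape technique or repeat reading for the waist. Section 7.8 says of blood pressure: "Blood pressure measurements will be taken three times, with a 1-minute interval between each measurement". It then has the systolic and diastolic results recorded, without saying which reading or average is meant.

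The results go on Screening 2 in Appendix 1. Under one subject header, the block beginning "ANTHROPOMETRIC EXAMINATION (PRE" is followed by an identical block beginning "ANTHROPOMETRIC EXAMINATION (POST". Each block is completed by a blood pressure line with one blank field, the second headed "BLOOD PRESSURE MEASUREMENT (POST". One sign-off closes the form: "Signature of officer after filling out form: Initials: Date". Neither block has a date of its own.

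The study is a single-arm before-after comparison (sections 1.1 and 4), analysed by a t-test, or by a Wilcoxon test where the data are not normal (section 8).

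**The concern.** The day-15 waist is written on the same form as the day-0 waist, by a team that knows the subject has just finished 14 days of tea. Section 2.3 cites reductions in weight, BMI and waist with green tea, so the hoped-for direction is known. An unstandardised tape reading leaves room for judgement. So does choosing one blood pressure result from three when the earlier result is in view. With no control arm, whatever enters the day-15 reading passes into the before-after change, and the analysis cannot separate it from an effect of tea. Waist, weight, BMI and blood pressure are the whole of the first specific aim.

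There is a smaller traceability point. One date and one signature cannot show on the form itself when each of two sets of measurements was made, or by whom. Sections 9.2 and 10.2 ask for records that allow reconstruction and verification against source.

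**Working it through.** **1. The two forms side by side (Appendix 1)**

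| Feature | Screening 2 (anthropometry, blood pressure) | Screening 3 (laboratory) |
|---|---|---|
| Day-0 and day-15 results | Same form, one block below the other | Separate initial and final parts |
| Subject header | One | One for each part |
| Signature and date | One, after the day-15 block | One for each part |
| Date or time of measurement | None in either block | One for each test |

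The page boundary is inferred from where headers and sign-off lines repeat. Screening 3 keeps its two parts separate in the same text, so the single sign-off on Screening 2 is unlikely to be a text-extraction artefact.

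**2. Is the baseline withheld anywhere?** Sections 7.5, 7.7, 7.8 and 10.3 were read for this. None masks the assessor, names an independent one or withholds the day-0 values. Section 10.3 keeps each subject's paper forms in one folder. The layout therefore makes the baseline visible and no procedure removes it. The documents do not say whether the form is in hand during the measurement, or whether the same officer attends both visits.

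**3. Which outcomes are exposed?** Section 1.1 lists 3 anthropometric measures, 2 blood pressures (systolic and diastolic), 5 glucose and lipid measures, 5 liver and renal measures, 5 haematology measures and 3 enzymes: 3 + 2 + 5 + 5 + 5 + 3 = 23. The last four groups are analyser-measured, kit-assayed or, for eGFR, calculated. Weight is a scale reading and BMI is calculated. That leaves the waist, and the choice among three readings for the two blood pressures: 3 of 23.

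**4. What would anchoring do?** Suppose each day-15 reading is pulled towards baseline by a fraction w. Each change d becomes (1 − w)d, so the mean and the SD of change are both multiplied by (1 − w), and t = mean/(SD/√n) does not move. Illustration with assumed values of n = 15, mean change 0.5 cm and SD 2.0 cm:

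- w = 0: t = 0.5 × √15 / 2.0 = 0.97
- w = 0.3: t = 0.35 × √15 / 1.4 = 0.97
- w = 0.6: t = 0.20 × √15 / 0.8 = 0.97

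The Wilcoxon signed ranks are also unchanged by a common factor. Proportional anchoring adds no false positives. It makes the reported change in cm too small, and the SD passed to a later trial too small by the same factor.

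**5. What would an expectation shift do?** This illustrates open assessment in general and does not measure the form. Two values of n are used: the plan's base of 15, and its total, 15/(1 − 0.20) = 18.75, rounded up to 19, which reproduces the figure in section 6. The documents give no SD, so the shift δ is expressed in SDs of the paired difference. The rejection probability of a two-sided 5% paired t-test, with true change zero, comes from the non-central t distribution with n − 1 degrees of freedom and non-centrality δ√n:

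| Assumed shift δ | n = 15 | n = 19 |
|---|---|---|
| 0.1 | 0.065 | 0.070 |
| 0.2 | 0.112 | 0.131 |
| 0.3 | 0.192 | 0.236 |
| 0.5 | 0.438 | 0.541 |

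No share of any row can be assigned to the page layout. The expectation comes from knowing that day 15 follows the tea, and a split form leaves that knowledge in place.

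**The case against.** **Visibility is not use.** A reader might infer that the officer does look at the baseline and that the day-15 values are therefore biased. The documents do not support that. Values could be taken first and transcribed later, or a different officer could attend. This objection stands, and *can see, with nothing to prevent it* is as far as the text goes.

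**The false-positive figures are not the cost of the form.** A reader might take the table of rejection rates as what the fix would save. Both the shift and its scale are assumed, and the mechanism is expectation, which is inherent in a single-arm before-after study. This also stands.

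**The two mechanisms differ.** Anchoring shrinks the change, while expectation may move it in the hoped-for direction, so no net direction can be claimed. This stands too.

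**The dates are not lost.** A reader might infer that the visit dates cannot be established. Sections 7.5 and 7.7 fix day 0 and day 15, and section 7.8 puts blood pressure on the day of blood sampling, which Screening 3 dates test by test. Section 10.1 requires examination results to be signed and dated. Section 10.3 requires a scan on the day of entry, which, if done after day 0, would date the first block. What remains is a missing per-visit date box and signature on one form.

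**Separate pages alone hide nothing.** Two pages in the same subject folder can still be read together. That is correct, so the split has to come with an instruction to keep the day-0 page out of view.

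**Conclusion.** The point holds as a minor matter of form design. Screening 2 makes the baseline visible at day 15, and no procedure in the protocol offsets this. The conclusion rests on the layout as it reads in Appendix 1 and on the absence of any masking or withholding provision. It needs no assumption about how officers behave.

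The exposure is narrow: waist circumference, and which of three blood pressure readings is entered. The size and direction of any bias are unknown, and the documents give no figure from which to estimate them. The point does not affect the sample size of 19, and it does not show that any result would be wrong. It deserves action because the remedy is nearly free, and a bias that enters at the visit cannot be removed at analysis.

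**What to change.** - Split Screening 2 into a day-0 page and a day-15 page, each with its own date, time and signature, as Screening 3 already does.
- Scan and file the day-0 page the same day under section 10.3, and keep it out of the folder used at the day-15 visit.
- State in sections 7.7 and 7.8 that the day-15 measurements are taken and recorded without the day-0 values on view.
- While the form is being redrawn, print a field for each of the three blood pressure readings and state in section 7.8, in advance, how they are combined. This removes the choice altogether.

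The cost is one extra form page and a few sentences, with no added visit, staff or measurement. The small downside is that a gross recording error would be caught at data entry and not at the visit. The change removes the visible anchor only. It does not blind the assessor to treatment, and it does not supply the missing waist method in section 7.7.

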The total number of subjects included in the study was 19, with an age range of 20-35 years (excluding women who were either unmarried or sexually inactive). These subjects resided in the vicinity of Padjadjaran University and had provided written consent by signing an informed consent form. The subjects must be in good health, have not been active smokers for a period of less than five years, and have no history of anaemia, cardiovascular disease, or liver and kidney disorders. The exclusion criteria employed are outlined below:

- a. Participants were required to take certain medications or vitamin supplements.
- b. The subjects reported experiencing discomfort during the administration of the product.
- c. Prior to the initiation of treatment, biochemical results were found to be outside the normal range.

Consent to Respondents

Informed consent will be requested by the research team before the washout period begins. Consent will be given in writing in the form of a signed consent form by the respondents.

Respondents Recruitment

The patient recruitment process was executed through the dissemination of advertisements utilising Google Forms, which were subsequently propagated via social media WhatsApp groups and Instagram. Following an initial screening process based on the information provided in the Google Forms by prospective research subjects, the research team made a selection based on inclusion criteria to obtain patients who met the specified criteria.

Test Product

The test product provided was 4 grams of white tea, packaged in a tea bag. The respondents were instructed to brew one tea bag in 200 mL of hot water for 10 minutes. The ingestion of the white tea should be scheduled for one hour prior to or two hours after breakfast.

Monitoring During Intervention

During the white tea intervention process, subjects will be monitored for food and beverage intake and daily activities. Please refer to Appendix 1 for a comprehensive overview of the daily data.

Research Duration

The research is estimated to take 28 days, including the first seven days for the washout phase, the second 14 days for the intervention phase, and the last seven days for the observational stage. This is to ensure that the subjects do not experience any serious effects as a result of the research.

Data Collection

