This study will analyze the potential effects of consuming white tea for 14 consecutive days. During the 7 days prior to white tea consumption (wash-out stage) and the 14 days during white tea consumption (treatment stage), all research subjects were instructed to avoid consuming products high in flavonoids, such as vitamins, herbal drinks containing spices (turmeric, ginger and kencur), fruits high in flavonoids (grapes, apples, oranges and their processed products), and products containing high levels of tannins (coffee, other types of tea, and chocolate). This was done to avoid excessive flavonoid intake, which can trigger anaemia and the formation of pro-oxidants. In addition, the presence of other strong antioxidants can also cause errors in the test (leading to bias) due to the influence of other antioxidant products. Furthermore, all respondents will be asked to drink white tea (made by brewing 4 grams of white tea in 200 mL of hot water) every morning one hour before eating or two hours after eating. To ensure the compliance of the research subjects, we will ask respondents to send videos of themselves consuming white tea, monitor and record the food and drinks consumed by all subjects in the CRF.

White tea is a type of tea that is believed to have better antioxidant content than other types of tea due to its high content of flavonoid compounds, especially catechins. If regular consumption of white tea for 14 days is proven to have a positive effect on anthropometric parameters, lipid profile, blood sugar levels and increases antioxidant enzyme activity, and is proven to be safe when reviewed from haematological parameters, ALT, AST, serum creatinine levels and eGFR, then this product can be further developed as a product for adjuvant therapy in various types of diseases. This study was conducted as an initial test of the potential of white tea for health before further exploration for application to a specific disease.

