2.3. Known Risks and Potential Health Benefits of White Tea Consumption

Possible risks associated with drinking white tea that have been studied:

- White tea contains theophylline and caffeine (17). Theophylline has been demonstrated to induce acid reflux, a factor which can precipitate the development of erosive oesophagitis. Consequently, the burning sensation experienced by the subject may be attributable to elevated levels of theophylline entering the body. The presence of caffeine in white tea has been demonstrated to induce adverse effects, including symptoms such as nausea and vomiting.
- Caffeine, a stimulant compound found in tea, has been observed to induce calcium release, thereby facilitating increased muscle contractions. Furthermore, it has been demonstrated that caffeine can induce the secretion of stimulatory agents such as prostaglandin, adenosine triphosphate, acetylcholine and nitric oxide from the urothelium, thereby stimulating augmented urine production in the bladder (18).
- Catechins, a type of polyphenol found in white tea, have been shown to possess therapeutic benefits in treating various diseases. However, in excessive doses, they have the potential to cause excessive pro-oxidant effects, triggering inflammatory reactions, necrosis and steatosis in the liver (18).
- The high polyphenol content of white tea has been demonstrated to have a potential inhibitory effect on iron absorption, which may consequently result in iron deficiency and the subsequent development of anaemia (19–21).

Benefits associated with drinking white tea that have been studied:

- Catechins and polysaccharides are believed to be responsible for the broad biological activity exhibited by white tea, which includes hypoglycaemic, hypolipidaemic, and antioxidant properties (13).
- The ingestion of green tea (*Camellia sinensis*) for a period of two months has been demonstrated to engender favourable outcomes in elderly subjects afflicted with metabolic syndrome. These outcomes encompass a reduction in weight, BMI, and waist circumference (22).
- The administration of three cups of green tea infusion (7.5 g/day) has been demonstrated to enhance the lipid profile in patients with T2DM nephropathy, without compromising renal function (23).

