AST	[] / [] / [] (DD/MM/YY) [] . [] WIB	$\mu\text{kat/L}$	 Eligible  Not Eligible
Creatinine	[] / [] / [] (DD/MM/YY) [] . [] WIB	$\mu\text{mol/L}$	 Eligible  Not Eligible
eGFR	[] / [] / [] (DD/MM/YY) [] . [] WIB	$\text{mL/min}/1.73\text{m}^2$	 Eligible  Not Eligible
Ureum	[] / [] / [] (DD/MM/YY) [] . [] WIB	mmol/L	 Eligible  Not Eligible
Antioxidant enzymes	[] / [] / [] (DD/MM/YY) [] . [] WIB	SOD: CAT: GPx:	 Eligible  Not Eligible

Signature of officer after filling out form:

Initials:

Date:

SAMPEL

Research Number:	Respondent's initials: []
------------------	----------------------------

b. Final Screening

Parameters	Test Date/Time	Result	Status
Hematology Profile	[] / [] / [] (DD/MM/YY) [] . [] WIB	RBC : $10^6/\mu\text{L}$ HB : g/dL HCT : % MCV : fL MCH : pg	 Eligible  Not Eligible
Lipid Profile	[] / [] / [] (DD/MM/YY) [] . [] WIB	TC : mmol/L HDL : mmol/L LDL : mmol/L Tg : mmol/L	 Eligible  Not Eligible
Fasting Blood Glucose	[] / [] / [] (DD/MM/YY) [] . [] WIB	mmol/L	 Eligible  Not Eligible
ALT	[] / [] / [] (DD/MM/YY) [] . [] WIB	$\mu\text{kat/L}$	 Eligible  Not Eligible
AST	[] / [] / [] (DD/MM/YY) [] . [] WIB	$\mu\text{kat/L}$	 Eligible  Not Eligible
Creatinine	[] / [] / [] (DD/MM/YY) [] . [] WIB	$\mu\text{mol/L}$	 Eligible  Not Eligible
eGFR	[] / [] / [] (DD/MM/YY) [] . [] WIB	$\text{mL/min}/1.73\text{m}^2$	 Eligible  Not Eligible
Ureum	[] / [] / [] (DD/MM/YY) [] . [] WIB	mmol/L	 Eligible  Not Eligible
Antioxidant enzymes	[] / [] / [] (DD/MM/YY) [] . [] WIB	SOD: CAT: GPx:	 Eligible  Not Eligible

Signature of officer after filling out form: Initials: Date:

SAMPEL

Research Number:	Respondent's initials: []
------------------	---

SKRINING 4 – MAKANAN, MINUMAN, KEGIATAN HARIAN DAN KELUHAN

Day-	Food Intake	Beverages / Supplement	Daily activity/ Complaint

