	
Lunch:
 
Dinner:
	
Indicate yes if applicable:
 
 Vitamin Yes / No* Indicate yes if applicable:
	
Are you experiencing any of the following? (Please indicate when the symptoms began.)
 
 Nausea  Vomiting  Constipation  Weakness  Loss of appetite  Fever  Excessive fatigue

10	
Breakfast:
 
Lunch:
 
Dinner:
	
 Fruit juice: Yes / No* Indicate yes if applicable:
 
 Vitamin Yes / No* Indicate yes if applicable:
	
Sleep duration: Activity:
 
Are you experiencing any of the following? (Please indicate when the symptoms began.)
 
 Nausea  Vomiting  Constipation  Weakness  Loss of appetite  Fever  Excessive fatigue

11	
Breakfast:
 
Lunch:
 
Dinner:
	
 Fruit juice: Yes / No* Indicate yes if applicable:
 
 Vitamin Yes / No* Indicate yes if applicable:
	
Sleep duration: Activity:
 
Are you experiencing any of the following? (Please indicate when the symptoms began.)
 
 Nausea  Vomiting  Constipation  Weakness  Loss of appetite  Fever  Excessive fatigue

Signature of officer after filling out form:

Initials:

Date:

SAMPLE

Research Number:		Respondent's initials: []	
12	Breakfast:	 Fruit juice: Yes / No* Indicate yes if applicable:	Sleep duration: Activity: Are you experiencing any of the following? (Please indicate when the symptoms began.)  Nausea  Vomiting  Constipation  Weakness  Loss of appetite  Fever  Excessive fatigue
	Lunch:	 Vitamin Yes / No* Indicate yes if applicable:	
	Dinner:		

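### The daily symptom question in Appendix 1 has no recall period, negative answer, severity or stop time, so resolved symptoms may go unrecorded and blank blocks cannot be interpreted

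*Combined protocol and SAP*

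**What the plan says.** Section 1.1 (Monitoring During Intervention) sends the reader to Appendix 1 for the daily data. There, Screening 4 has one row per day for 28 days. The symptom question sits in a column headed "Daily activity/ Complaint", together with sleep duration and activity. It reads "Are you experiencing any of the following? (Please indicate when the symptoms began" and is followed by tick boxes for nausea, vomiting, constipation, weakness, loss of appetite, fever and excessive fatigue. The wording is the same on every row. In the neighbouring column, fruit juice and vitamins can be answered either way, for example "Vitamin Yes / No* Indicate yes if applicable".

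Other sections that bear on the point:

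- Section 1.2 has the tea drunk "every morning one hour before eating or two hours after eating". Sections 1.1 and 7.4 also place it around breakfast.
- Section 2.3 warns that caffeine in the tea can "induce adverse effects, including symptoms such as nausea and vomiting".
- Section 7.5 has researchers record "any complaints that may be experienced by the subjects, whether related or unrelated to the administration of white tea products".
- Section 1.1 (Research Duration) gives the reason for the three-phase schedule, which ends with the observation week: "This is to ensure that the subjects do not experience any serious effects as a result of the research".
- Sections 9.1 and 10.2 provide for data validation, clarification forms and queries on missing or unclear data.

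**The concern.** The issue is how the listed symptoms are asked, not which symptoms are listed. A present-tense question without a recall period does not clearly ask about a symptom that came and went. Nausea or vomiting soon after a morning drink is just that kind of symptom, and section 2.3 names both as known risks. The prompt for onset asks when a symptom started. It does not bring in one that has already ended.

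The block also has no negative answer. If it is empty, the form does not show whether the subject was asked and had nothing, or was not asked. And with no severity or stop time, a ticked box cannot separate a passing complaint from one that matters.

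Blood tests, anthropometry and blood pressure are taken only on days 0 and 15. Between those days and through the observation week, Screening 4 is the only structured symptom record that the plan provides. If it under-records, a report that subjects had no complaints would owe something to the form.

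**Working it through.** The documents state no figure for this point, so there is none to reproduce. The check is a reading of the form against the text, followed by an illustration with assumed values.

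**Reading the form**

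1. *Recall.* All 28 rows use the present tense. None gives a period such as the day or the time since the last entry. No entry time is fixed anywhere. The gap does not depend on one: whenever the single daily answer is given, a symptom that has already resolved is not clearly asked for.
2. *Negative answer.* Juice and vitamins have Yes / No on the same row, and the history table in Screening 1 has Yes / No / Unknown. The symptom block has tick boxes only. With 19 subjects and 28 days there are 19 × 28 = 532 such blocks, of which 19 × 14 = 266 fall on tea days.
3. *Queries.* Section 10.2 has missing or unclear data queried, and section 9.1 provides double entry or full checking. Neither can pick out an unanswered block, because it looks the same as a symptom-free one. The officer's signature stands at the foot of a page that covers several days, so it does not confirm each day.
4. *Severity and end.* Neither is on the form.

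**Illustration of direction**

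Input from the documents: n = 19 (section 6; 15 / (1 − 0.20) = 18.75, rounded up). Assumed: a true share p of subjects with a short-lived symptom, and a share s of those subjects whose symptom is captured. The chance that at least one case is recorded is 1 − (1 − p·s)^n. With p = 10%:

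| Captured share s | 19 subjects | 15 completers |
|---|---|---|
| 100% | 1 − 0.900^19 = 86% | 79% |
| 75% | 1 − 0.925^19 = 77% | 69% |
| 50% | 1 − 0.950^19 = 62% | 54% |
| 25% | 1 − 0.975^19 = 38% | 32% |

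The result is sensitive to the number of episodes. Take p = 20%, so that with full capture the chance of recording no case is 0.80^19 = 1.4%.

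- One episode per affected subject, 70% captured: 0.20 × 0.70 = 0.14, and 0.86^19 = 5.7%.
- One episode, 30% captured: 0.20 × 0.30 = 0.06, and 0.94^19 = 31%.
- Three independent episodes, each 30% captured: an affected subject is recorded with probability 1 − 0.7^3 = 0.657. Then 0.20 × 0.657 = 0.131, and 0.869^19 is about 7%.

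**Denominator**

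If no case were reported, the two-sided 95% upper limit would be 1 − 0.025^(1/19) = 17.6% with 19 subjects asked, and 1 − 0.025^(1/15) = 21.8% if only 15 had been. The form cannot show which applies.

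**The case against.** The strongest reply has five parts.

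- *Entry time.* A reader might infer from the dinner field that the row is completed in the evening, long after the tea. The documents do not support that. Dinner is in the food column, symptoms are in another, and the symptom cell also holds sleep duration, which is known in the morning. Different cells may be filled at different times.
- *Wording.* Screening 4 keeps an Indonesian heading, so the English may be a translation, and a daily row headed as a complaint record can be read as covering the day. This is fair. It means that resolved symptoms *may* be missed, not that they *are* missed.
- *Blanks.* A reader might infer that blanks will be counted as no effect. No section says so, section 7.3 asks for exhaustive completion, and section 10.2 provides for queries. What stands is narrower: the form does not let anyone see which blanks to query.
- *Other safety sources.* A reader might call this form the only safety record on tea days. Section 7.5 separately obliges researchers to record any complaint, without restricting it to the seven boxes, and section 10.4 audits side effects against source documents. That is a real but partial mitigation, since the form named for daily data does not clearly ask for resolved complaints. The morning video in section 7.4 is for compliance, and no symptom question is attached to it.
- *Relevance.* Section 1.1 defines the safety evaluation by haematology, liver and renal tests, and section 8 plans only before-after tests and no symptom rate. So no planned result fails. Nor does the argument reach every risk in section 2.3: the liver effects and anaemia named there are covered by laboratory tests, and burning and increased urination are not on the list. Only nausea and vomiting fit it.

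**Conclusion.** The point holds as a weakness of the form. With no recall period, negative answer, severity or stop time, nausea or vomiting that resolves before entry may go unrecorded, and a symptom-free day cannot be told from an unanswered one. The direction is towards under-recording. The size is unknown: the percentages above rest wholly on assumed incidence, capture and number of episodes, and moving from one episode to three cuts the 31% to about 7%.

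The before-after laboratory comparisons and the sample size are not affected. What is weakened is any statement that subjects had no complaints or deleterious effects during the tea and observation phases, which is the stated purpose of the observation week in section 1.1. The form should be changed before data collection, because the missing answers cannot be recovered afterwards. It is not a fault that undermines the study.

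**What to change.** On every row of Screening 4:

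1. Replace the question with: *Since the last entry, have you had any of the following, even if it has now gone?*
2. Add a 'No complaint' box, or Yes / No for each symptom.
3. For each ticked symptom, add start and stop time (or ongoing) and mild / moderate / severe.

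In sections 7.5 and 9.1, state that a block with neither a symptom nor 'No complaint' marked is missing and is to be queried. In section 8, state that any symptom frequency reported uses only subject-days with an explicit answer.

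The cost is rewording and reprinting one form and a few more seconds per entry. Symptom counts may look less favourable than they would with the present wording. The intervention, the visits and the planned tests do not change.
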